12.7.2 Exploratory Analyses

12.7.3 Other Safety Variables and Analyses

Other safety variables will be analyzed for the Safety Population.

In addition to the Investigator's evaluation of normal or abnormal, the Sponsor will internally evaluate clinical laboratory, vital-sign, and ECG results for an outlying result or extreme value as follows:

- An outlying result for any numeric laboratory result, vital-sign result, or ECG interval measurement will be any post-administration change from baseline that meets either of the following criteria:
 $<25\text{th Percentile} - 1.5 * (\text{interquartile range})$ OR
 $>75\text{th Percentile} + 1.5 * (\text{interquartile range})$.
- An extreme value for any numeric laboratory result, vital-sign result, or ECG interval measurement will be any post-administration change from baseline that meets either of the following criteria:
 $<25\text{th Percentile} - 3 * (\text{interquartile range})$ OR
 $>75\text{th Percentile} + 3 * (\text{interquartile range})$.

Post-administration changes from baseline will be summarized by mean, SD, minimum, and maximum at each time point for each treatment group (CECT vs NECT). Plots and shift tables of all post-administration changes from baseline vs time will be generated and examined for trends and relatively large individual changes from baseline.

12.7.3.1 Clinical Laboratory Evaluation

Descriptive statistics will be displayed for the observed values and changes from baseline. In addition, for each clinical laboratory variable and each time point, the following safety endpoints will be summarized by counts and percentages by treatment group (CECT vs NECT):

- The occurrence of 1 or more changes from baseline, at each post-administration time point, greater than 40% and 80% of the span of the normal limits (not applicable to qualitative parameters).
- The occurrence of post-administration values outside the normal limits (not applicable to qualitative parameters). Shift tables based on the normal range will be prepared.

12.7.3.2 Vital Signs

Descriptive statistics will be displayed for the observed values and changes from baseline. For each vital-sign variable and each time point, the following safety endpoints will be summarized by counts and percentages by treatment group (CECT vs NECT):

- The occurrence of 1 or more changes from baseline, at each post-administration time point, greater than a prespecified magnitude (20 mm Hg for systolic blood pressure, 10 mm Hg for diastolic blood pressure, 10 beats/minute for heart rate and 10 breaths/minute for respiration rate).

- The occurrence of post-administration values outside the normal limits (Section 15.3). Shift tables based on the normal range will be prepared.

12.7.3.3 Physical Examination

The number and percentage of patients with changes in physical examination status from normal at baseline to abnormal at each post-administration time point (and vice versa) will be presented by treatment group (CECT vs NECT). Shift tables based on the normal range will be prepared.

12.7.3.4 Adverse Events

AEs and SAEs will be coded using MedDRA and all reported events will be listed for the safety population. Treatment-emergent AEs are defined as AEs that occur from the time of treatment administration through Follow-Up 3. The number and percentage of patients with 1 or more AEs will be summarized by system organ class and preferred term overall and by treatment group (CECT vs NECT). Summaries will also be presented by AE intensity and judged relationship to Visipaque™ or saline placebo. Treatment-emergent SAEs are defined as SAEs that occur from the time of treatment administration through Follow-Up 3. Treatment-emergent SAEs will be presented by treatment group for the safety population.

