
Name of Sponsor/Company: GE Healthcare Ltd. and its Affiliates	Individual Study Table Referring to Part of Dossier in Which the Individual Study or Study Table is Presented:	(For National Authority Use Only)
Name of Finished Product: Visipaque™ Injection 320 mgI/mL	Volume:	
Name of Active Ingredient: Iodixanol	Reference:	

For a randomly selected subset of 5% of the patients (N=29 in each arm), the images will undergo a second blinded visual assessment by the same reader. Intra-reader (within-reader) agreement for these blinded visual image assessments will be measured by percentage agreement. A percentage agreement with an exact 95% CI will be determined for each reader comparison and all readers for subjects with re-reads of images. In cases where images are re-read, it is the result of the first read that is to be included in the image quality/diagnostic confidence summaries.
		

Exploratory Analyses:
 
[REDACTED]
 
[REDACTED]
 
[REDACTED]
 
[REDACTED]
 
[REDACTED]
 
[REDACTED]
 
[REDACTED]
		

Safety Analyses:
 
Incidence rate of adverse clinical events assessed at 6 months, the mean change from baseline to post-baseline vital signs, and the physical examinations will be summarized for the 2 treatment groups.
		

Sample Size Estimation:
 
The primary endpoint is the incidence rate (proportion) of AKI stage ≥ 1 (by AKIN SCr criteria) at 48 hours after intervention in patients with stage III or stage IV CKD. With P1 defined as the incidence rate of AKI stage ≥ 1 following i.v. administration of Visipaque™ and P2 defined as the incidence rate of AKI stage ≥ 1 following administration of placebo, the sample size estimate is based on the following assumptions and statistical method:
		

 • Both P1 and P2 are 10% • A noninferiority margin of 5% • Power of 80% using the 95% CI of P1 – P2 • The score test [Miettinen and Nurminen 1985] with a 1-sided 0.025 significance level is employed 		

A sample size of 1164 randomized patients (582 per treatment group) in the FAS will provide 80% power to demonstrate noninferiority of the proportion of AKI stage ≥ 1 (by AKIN criteria) in patients receiving Visipaque™ Injection 320 mgI/mL as compared with patients receiving the saline placebo.
		

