Follow-ups will occur at 48 hours, 7 days, and 6 months post-baseline. At Follow-up 1 (48 hours \pm 6 hours), blood samples will be collected either at the patient's home (if this service is locally available) or at the study center and concomitant medications, adverse events (AEs), serious adverse events (SAEs) and critical events recorded (by telephone if the patient receives a home visit). If Nephrocheck® biomarker analysis will be performed, urine samples will be collected. Follow-up 2 (7 days \pm 2 days) will be a clinic visit for those patients who meet primary criteria (AKI stage \geq 1, per AKIN) at Follow-up 1 and a telephone follow-up for all other patients. If the patient attends the clinic, blood samples for clinical chemistry will be collected and concomitant medication, vital signs, physical examination, AEs, SAEs and critical events will be recorded. If the patient receives a telephone follow-up, concomitant medication, AEs, SAEs and critical events will be recorded. At Follow-up 3 (6 months \pm 2 weeks), a blood sample for SCr will be collected either at the patient's home (if this service is locally available) or at the study center and concomitant medications, AEs, SAEs and critical events will be recorded (by telephone for patients receiving a home visit).

Study critical events will be adjudicated by a Critical Events Adjudication Committee (CEAC; Section 9.7). A Data Safety Monitoring Board (DSMB) will review and evaluate safety data periodically throughout the study (Section 9.8).

An overview of the study design is presented in [Figure 1](#).

A subset of patients (no more than 100), at selected sites in the USA, may also receive the inert fluorescent agent MB-102 (manufactured by MediBeacon, Saint Louis, MO, USA) and will be monitored by ORFM (Sections 8.1.3 and 9.2.3).

Figure 1 Study Diagram

AKI = Acute kidney injury

CECT = Contrast-enhanced computed tomography

CKD = Chronic kidney disease

EVAR = Endovascular aneurysm repair

NECT = Non-enhanced computed tomography

R = Randomization

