If the laboratory test results obtained at Follow-up 1 meet primary criteria (AKI stage ≥ 1 , per AKIN), a clinic visit will be scheduled 7 days ± 2 days after the Baseline Visit. All other patients will receive a telephone follow-up at 7 days ± 2 days after the Baseline Visit.

If the patient attends the clinic, the following will be collected and/or performed:

- Concomitant medication.
- Vital signs (blood pressure, heart rate, respiration rate) in the sitting position.
- Blood samples for SCr, cystatin C, and N-GAL (central laboratory analysis).
- Physical examination.
- AEs, SAEs and critical events, including EVAR-related post-baseline events.

If the patient receives a telephone follow-up, the following will be recorded:

- Concomitant medication.
- AEs, SAEs and critical events, including EVAR-related post-baseline events.

See Section 10.2 and the Study Schedule of Events Table (Table 1) for further details.

9.5 Follow-up 3

At 6 months ± 2 weeks after the Baseline Visit, a blood sample for SCr will be collected either at the patient's home (if this service is locally available) or at the study center.

Concomitant medications, AEs, SAEs, and critical events (including EVAR-related post-baseline events) will be recorded either by telephone (for patients receiving a home visit) or at the study center.

See Section 10.2 and the Study Schedule of Events Table ([Table 1](#)) for further details.

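### Adverse events after a single injection are tabulated only over dosing to 6 months; tables by time of onset should be added so that an early excess can be seen

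*Combined protocol and SAP*

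**What the plan says.** Section 12.7.3.4 defines the window for AEs as "Treatment-emergent AEs are defined as AEs that occur from the time of treatment administration through Follow-Up 3" and repeats it for serious events: "Treatment-emergent SAEs are defined as SAEs that occur from the time of treatment administration through Follow-Up 3". The synopsis, under Safety Analyses, agrees: "Incidence rate of adverse clinical events assessed at 6 months". Section 12.7.3.4 tabulates patients with events by system organ class and preferred term, overall and by arm. It adds: "Summaries will also be presented by AE intensity and judged relationship to Visipaque™ or saline placebo". It also says that "all reported events will be listed for the safety population". Nothing is cut by time of onset.

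Exposure is one administration of 100 mL of contrast or saline (Sections 8.1.1, 8.1.2 and 8.3). Contacts are more frequent than the table window: "Follow-ups will occur at 48 hours, 7 days, and 6 months post-baseline" (Section 6.1), and Table 1 also records AEs post-scan. At 7 days the contact depends on the creatinine result. Patients meeting AKIN stage 1 or higher attend the clinic; for the rest, Section 9.4 says "All other patients will receive a telephone follow-up at 7 days ± 2 days after the Baseline Visit".

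**The concern.** An acute reaction to contrast would appear soon after the injection. Sections 9.2 and 10.2.6 recognise this by requiring staff trained in emergencies to be at hand for 30 minutes after dosing. Yet the AE tables count a reaction on the day of the scan and an unrelated illness months later in the same cell. A patient who has both counts once, exactly like a control patient who has only the later illness. The early difference between arms therefore shrinks, and the larger background makes it less precise.

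The rest of Section 12.7.3 is handled differently: laboratory values, vital signs and physical examination are summarized at each post-administration time point. AEs are the exception. The trial's stated objective is to demonstrate safety, so low sensitivity to early non-renal events matters for how the AE tables will be read.

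The AKI row of the AE table can mix early and late events too. Section 10.2.6 requires an AE for a creatinine rise of at least 0.3 mg/dL from baseline and/or the previous result, and creatinine is measured again at 6 months. The 48-hour AKI analysis stands separately, so this affects only how the AE table reads.

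**Working it through.** **Arm size.** The only design figure needed is 582 per arm (Section 12.8: 10% in both arms, margin 5 points, one-sided 0.025, 80% power, score test). It reproduces:

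- Unpooled variance: n = 2 × 0.10 × 0.90 × (1.960 + 0.842)² / 0.05² = 566 per arm.
- Score test: the rates restricted to a 5-point difference are 13.03% and 8.03%, so s0 = √(0.1303 × 0.8697 + 0.0803 × 0.9197) = 0.4326 and s1 = √(2 × 0.09) = 0.4243. Then n = [(1.960 × 0.4326 + 0.842 × 0.4243) / 0.05]² = 581 per arm.
- Exact Miettinen-Nurminen power at 582 per arm is 80.5%.

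**Share of the window.** Taking 6 months as 182.5 days, the first 48 hours are 2/182.5 = 1.1% of it and the first 7 days are 7/182.5 = 3.8%.

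**Assumptions.** The documents give no AE rates. Assume that a share B of control patients has any AE by 6 months, at a constant hazard, and that contrast adds an independent early risk of 3%. Then, for a table running from dosing to day d:

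- control: c = 1 − (1 − B)^(d/182.5)
- contrast: t = 1 − (1 − c)(0.97), so the visible difference is 0.03 × (1 − c)
- SE = √{[c(1 − c) + t(1 − t)]/582}
- power = Φ[(t − c − 1.96 × SE0)/SE], where SE0 uses the pooled rate; two-sided 0.05

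Example with B = 50%. At 48 hours c = 0.76%, t = 3.73%, difference 2.98 points and SE 0.86. SE0 is 0.87, so power = Φ[(2.98 − 1.96 × 0.87)/0.86] = 93%. At 6 months the rates are 50% and 51.5%, difference 1.5 points, SE and SE0 both 2.93, and power = Φ[(1.5 − 1.96 × 2.93)/2.93] = 7%.

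| 6-month background | Table | Control | Contrast | Difference (points) | SE (points) | Power |
|---|---|---|---|---|---|---|
| 30% | 0-48 h | 0.4% | 3.4% | 3.0 | 0.79 | 96% |
| 30% | 0-7 days | 1.4% | 4.3% | 3.0 | 0.97 | 86% |
| 30% | 6 months | 30.0% | 32.1% | 2.1 | 2.71 | 12% |
| 50% | 0-48 h | 0.8% | 3.7% | 3.0 | 0.86 | 93% |
| 50% | 0-7 days | 2.6% | 5.5% | 2.9 | 1.16 | 71% |
| 50% | 6 months | 50.0% | 51.5% | 1.5 | 2.93 | 7% |
| 70% | 0-48 h | 1.3% | 4.3% | 3.0 | 0.96 | 87% |
| 70% | 0-7 days | 4.5% | 7.4% | 2.9 | 1.38 | 54% |
| 70% | 6 months | 70.0% | 70.9% | 0.9 | 2.67 | 5% |

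The plan tests no AE difference, so power here only measures sensitivity. In terms of precision, 1.96 × SE is 1.6 to 1.9 points at 48 hours and 5.2 to 5.7 points at 6 months.

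**Sensitivity to the assumptions.**

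- Larger excess: with 5% and the same backgrounds, power is about 99% or more at 48 hours and 8% to 25% at 6 months.
- Heavier early background, dropping the constant hazard: 5% of controls have an AE within 48 hours and contrast adds 5%. The 48-hour comparison is 1 − 0.95 × 0.95 = 9.75% against 5%, power about 88%. At 6 months, 62% against 60% gives about 11%, and 33.5% against 30% about 25%.
- Single preferred term, 2% excess, 6-month background 0.5% / 2% / 5% / 10%: power at 6 months is 80% / 50% / 28% / 17%, against 90% to 93% at 48 hours. Rare terms lose little; common terms lose most of their sensitivity.

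**The case against.** There is a fair case that little is missing.

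- **Other outputs exist.** Preferred-term tables show typical acute terms, the relationship table is meant to separate contrast events from other illness, and every event is listed. This stands in part, and it rules out the reading that early events are lost. But the study is not blinded (Section 8.4), so causality is judged with the arm known, and a listing is not a comparison between arms.
- **The main early risk is analysed early.** AKI at 48 hours is the primary endpoint, three further 48-hour AKI endpoints are tested, and a 30% or greater fall in eGFR at 48 hours is analysed. This stands and limits the gap mainly to non-renal acute events.
- **Six months has a purpose.** Section 6.3 justifies it by late-appearing effects. This stands, and is a reason to keep the 6-month table.
- **Serious acute reactions are too rare to compare.** Section 6.3 cites 0.01% to 0.02% for low-osmolar media, or 582 × 0.0001 to 582 × 0.0002 = 0.06 to 0.12 expected events in an arm. No window helps there. The gain is for milder, more frequent events.
- **A SAP may add the table.** Sections 12.6.3 and 12.8 to 12.10 defer details to a SAP. Section 12.7.3.4 does not, and the text available contains no such table, but one could be specified there.

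A reader might infer that the long window biases the trial towards finding no difference. The documents do not support that. Both arms share the window, the AE tables carry no test or margin, and noninferiority rests only on the AKI interval in Section 12.6.2. A reader might also blame an elderly population; eligibility is age 18 or over, and no age distribution or AE rate is given.

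**Conclusion.** The point holds as a modest gap in the safety tables. One 6-month window is the only AE and SAE window stated, and it makes the overall, intensity and common-term tables insensitive to an early excess. Under the assumed 3-point excess and 30% to 70% background, power falls from about 87-96% in a 48-hour table to 5-12% at 6 months. The direction is the same under every assumption tried; the size depends on rates the documents do not give, and the loss is small for rare terms. No endpoint, sample size or primary conclusion changes.

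It might seem to follow that the treatment-emergent window should end at Follow-up 2. That does not hold up. The visit falls anywhere from day 5 to day 9, and it is a clinic visit only for patients who met the AKI criteria. AE ascertainment in such a window would depend on the primary outcome. Collection up to Follow-up 1 does not have this defect.

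**What to change.** Keep the 6-month treatment-emergent definition and table. Add to Section 12.7.3.4 AE and SAE tables by arm by fixed onset time since dosing: 0-48 hours, over 48 hours to 7 days, and after 7 days. Give the between-arm difference with a 95% CI for each, labelled descriptive.

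Name the 0-48 hour table as the main early display, and note beside the later tables that contact at 7 days differs by AKI status. Follow-up 1 may fall at 42 hours, so a few events before 48 hours will be reported only at the next contact. Section 8.7 records the time of dosing. The protocol does not say whether AE onset is recorded to the hour; if only dates are held, state the calendar-day rule in advance.

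The cost is a few extra descriptive tables with intervals unadjusted for multiplicity. There are no new visits or samples, and no effect on alpha or sample size. Early reports will still come from an unblinded study, which the tables should acknowledge.

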12.8 Sample Size Calculation

The primary endpoint is the incidence rate (proportion) of AKI stage ≥ 1 (by AKIN SCr criteria) at 48 hours after intervention in patients with stage III or stage IV CKD. With P1 defined as the incidence rate of AKI stage ≥ 1 following i.v. administration of Visipaque™ and P2 defined as the incidence rate of AKI stage ≥ 1 following administration of saline placebo, the sample size estimate is based on the following assumptions and statistical method:

- (1) Both P1 and P2 are 10%
- (2) A noninferiority margin of 5%
- (3) Power of 80% using the 95% CI of P1 – P2
- (4) The score test [Miettinen and Nurminen 1985] with a 1-sided 0.025 significance level is employed

A sample size of 1164 randomized patients (582 per treatment group) in the FAS will provide 80% power to demonstrate noninferiority of the proportion of AKI stage ≥ 1 (by AKIN criteria) in patients receiving Visipaque™ Injection 320 mgI/mL as compared with patients receiving the saline placebo.

To compensate for a screen failure rate of approximately 15%, approximately 1370 patients will be screened.

It is expected that the number of patients who are excluded from the PP set will be small, resulting in minimal loss of statistical power. However, the number of patients excluded from

the PP set will be monitored and the sample size may be increased as needed to maintain adequate statistical power to repeat the primary analysis in the PP set.

A blinded sample size re-estimation will be performed after 50% of patients are enrolled and adjudicated by the CEAC. The calculation will be made by an independent statistician and will be based on the blinded, overall rate of AKI as determined by the CEAC. The purpose of this re-evaluation is to confirm assumptions made about the rate of AKI in the planned sample size calculation. No re-estimation of the difference between treatments or the NI margin will be done. In a blinded sample size re-estimation of the overall event rate in a non-inferiority trial with a binary endpoint, there is no notable effect on the Type I error rate [Friede et al. 2007] and, therefore, no alpha adjustments will be made in the final analysis. Based on the results of the re-estimation, the Steering Committee may recommend to stop enrollment if the new sample size is already exceeded, continue with the planned sample size, or increase the sample size to maintain adequate statistical power. Details of the sample size re-estimation methodology will be pre-defined in the SAP.

12.9 Procedures for Missing, Unused, and Spurious Data

Missing values will not be substituted by estimated values but treated as missing in the statistical evaluation unless otherwise specified in the SAP. All data from all patients dosed in the study will be included in all listings, plots, summary tables, and statistical analyses when appropriate.

12.10 Rules for Excluding Patients from Analysis

All randomized patients with any post-randomization observations will be included in the analyses unless otherwise specified in the SAP. The Sponsor will make any decisions regarding whether any patients or any individual values belonging to a patient will be excluded from the evaluations when the protocol violation is considered to have a negative impact on the scientific aspects and interpretation of the study results. Such judgments should be made in a blinded fashion before database lock and before any analyses have been performed. If the patient has been randomized to receive Visipaque™ or saline placebo and has post-randomization observations, all available safety data will be used. The reason(s) for any exclusion will be described in the report.

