8.4 Blinding

This study is not blinded.

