9.2.1 Image Acquisition

Contrast-enhanced and nonenhanced CT images will be acquired in accordance with the CT Imaging Manual. The appropriate study personnel shall deliver the dose of Visipaque™ 320 mg I/mL or the saline placebo dose. The entire contents of the 100 mL of Visipaque™ 320 mg I/mL or saline placebo should be administered and followed by a 10 mL saline flush. The administration should be timed properly in accordance with the Imaging Manual to provide an optimal arterial and delayed venous phase following the nonenhanced phase.

All CECT image sets from the treatment group and NECT image sets from the placebo group will be sent to the Sponsor in DICOM format. These image sets will also be archived at the clinical site in accordance with the CT Imaging Manual.

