10.2 Safety Assessments

The Investigator(s) and the Sponsor/CRO will review the safety data. The following safety data will be collected and evaluated:

- Clinical laboratory parameters: clinical chemistry, hematology, biomarkers and urinalysis ([Table 2](#)).
- Vital signs: systolic/diastolic blood pressure, respiration rate, heart rate.
- 12-lead ECG (screening only).
- Physical examination.
- AEs and SAEs.
- Pre-specified normal limits for vital signs are provided in Section [15.3](#).

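### Section 12.10 lets the Sponsor exclude patients or single values for protocol violations without confining this to the per-protocol set, and its blinded-judgment condition has no stated means in an open-label study

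*Combined protocol and SAP*

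**What the plan says.** Section 12.10 starts from inclusion of randomized patients with post-randomization observations, unless the SAP specifies otherwise. It then gives the Sponsor a power of exclusion: "The Sponsor will make any decisions regarding whether any patients or any individual values belonging to a patient will be excluded from the evaluations". The trigger is "when the protocol violation is considered to have a negative impact on the scientific aspects and interpretation of the study results". Three conditions follow. On process, "Such judgments should be made in a blinded fashion before database lock and before any analyses have been performed". For randomized patients with post-randomization observations, "all available safety data will be used". Reasons for exclusions are to be reported.

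Section 12.3.2 defines the FAS by dosing plus a baseline and a post-scan SCr, with patients analyzed as randomized. It contains no exclusion for deviations, and it makes the FAS the set for the primary analysis. Section 12.3.3 defines the PP set, which removes patients with major deviations and patients with specified off-protocol contrast exposure before Follow-up 1.

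Section 8.4 reads: "This study is not blinded".

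**The concern.** Two features combine. First, the power in 12.10 covers the evaluations in general and extends to single values. Section 12.6.3 does not impute missing values unless the SAP says otherwise, so excluding one 48-hour SCr removes that patient's primary outcome. This would put a second, discretionary deviation filter over a set that 12.3.2 defines without one.

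Second, the protection against biased use of that filter is blinded judgment, in a study where treatment is open. The Synopsis keeps unblinded data from the Steering Committee and the adjudication committee; it does not mention the Sponsor. If someone who knew both the arm and the post-scan SCr made the decisions, the FAS would no longer protect the noninferiority comparison against selection.

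**Working it through.** **Text.** Who could know the arm:
- Section 8.2: the Sponsor or CRO performs allocation.
- Section 8.7: vial code, volume, date and time of administration go into the eCRF.
- Section 9.2.1: contrast-enhanced and nonenhanced image sets "will be sent to the Sponsor in DICOM format".
- Section 12: the Sponsor and/or CRO analyzes the data.

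None of these says that the people who decide exclusions see this information. None says that they do not. Section 12.8 assigns the sample size re-estimation to an independent statistician; 12.10 names no comparable person or procedure.

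**Reproducing the plan's figure.** Inputs from 12.8: 10% in both arms, margin 0.05, one-sided 0.025, 80% power, score test. The restricted estimates on the margin are 0.1303 and 0.0803.
- s0 = √(0.1303×0.8697 + 0.0803×0.9197) = 0.4326
- s1 = √(2×0.10×0.90) = 0.4243
- n = [(1.960×0.4326 + 0.8416×0.4243)/0.05]² = 580.7, so 581 per arm

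The plan states 582. Exact power of the Miettinen–Nurminen test at 582 per arm is 80.5%, so the stated size is reproduced.

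**How few values can matter.** The event counts here are assumed, not taken from the documents. The statistic is z = (p1 − p2 − 0.05)/SE, with the restricted-variance SE and the factor N/(N − 1). Noninferiority requires z < −1.96.

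| Contrast | Control | Difference | SE | z | Upper 95% bound | Result |
|---|---|---|---|---|---|---|
| 66/582 | 58/582 | 1.37% | 0.01830 | −1.98 | 4.96% | pass |
| 67/582 | 58/582 | 1.55% | 0.01835 | −1.88 | 5.15% | fail |
| 66/581 (one event removed from 67) | 58/582 | 1.39% | 0.01832 | −1.97 | 4.98% | pass |

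**Error rate on the margin.** True rates are set at 15% versus 10%, with 582 per arm. The rejection probability is summed exactly over both binomial distributions after the stated removals.

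| Removal | One-sided error |
|---|---|
| None | 2.5% |
| 1 contrast-arm event | 3.0% |
| 3 contrast-arm events | 4.3% |
| 5 contrast-arm events | 6.0% |
| 3 events from each arm | 2.6% |
| 3 contrast-arm patients regardless of outcome | 2.5% |

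The inflation comes from removal that depends on both arm and outcome. The number removed does not produce it alone.

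**The case against.** The case for leaving 12.10 as it stands has several parts.

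- *The power is conditioned.* It needs a protocol violation judged harmful, a blinded judgment before lock and before analysis, and reported reasons. This stands, and it rules out reading 12.10 as a free hand over any evaluation. The trigger is still a judgment without a list of qualifying violations, and a pre-lock deadline does not mask an open database.
- *Open-label treatment does not prevent blinded review.* The protocol has blinded adjudication (9.7), blinded image reading (9.9) and blinded sample size re-estimation (12.8). This stands too. A reader might infer that the deciders know the arm, or that the images reach the Sponsor labelled by arm. The documents support neither. Section 9.2.1 says only that both kinds of image set are sent, and 13.2.4 requires identification codes. Contrast would be visible to anyone viewing an image, but nothing links viewers to exclusion decisions.
- *The creatinine values may already be protected as safety data.* Section 10.2 lists "Clinical laboratory parameters: clinical chemistry, hematology, biomarkers and urinalysis" among safety data, Table 2 places SCr under clinical chemistry, and the primary objective is a safety objective. This is arguable but not settled, because the primary test runs in the FAS and not in the safety population.
- *The specific definition in 12.3.2 may control.* No precedence is stated, so 12.10 cannot be said to override it. It equally cannot be said to yield.
- *The SAP may supply the procedure.* Section 12.10 defers to a SAP, and the text reviewed contains no separate SAP section. A masking procedure there cannot be ruled out.

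**Conclusion.** The concern holds in a limited form. Section 12.10 does not confine violation-based exclusions to the PP set, so on its wording they can reach primary SCr values in the FAS. Its blinding condition has no stated means of being met. Knowledge of the arm by the deciders is possible and has not been shown.

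The calculations are a worst-case illustration and do not forecast what would happen. The rise from 2.5% to about 4.3% assumes true rates on the margin, 582 per arm, and three exclusions that are all contrast-arm events. Blinded judgment, if achieved, would prevent that pattern. A reader might take the reversal at 67 events as a special weakness of this trial; any threshold test has such a point, and 66 versus 58 is not the design assumption of equal 10% rates.

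The point is more than missing detail, because the rule as written leaves the boundary between FAS and PP set open. It should be corrected before lock.

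**What to change.** Amend 12.10, and the SAP to match, as follows.

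1. Exclusions for protocol violations apply to the PP set only. No patient who meets the 12.3.2 definition, and no reported central-laboratory SCr value, is removed from the FAS for a protocol violation.
2. The contrast-exposure exclusions of 12.3.3 depend on arm and dosing and cannot be made fully masked. Apply them as a fixed, programmed rule.
3. The remaining judgment-based PP deviations are classified and signed off before lock by named reviewers. The reviewers are masked to post-scan SCr and, where the deviation does not itself reveal it, to arm. Their listings omit allocation, administration records and images accordingly.

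The cost is a wording change plus preparation of masked review listings. The sample size stays at 1164, and the primary test and margin are unchanged.
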